EFFECTIVENESS OF A BRIEF INFORMATION ABOUT ADVANCE DIRECTIVES IN PRIMARY CARE: A RANDOMIZED CLINICAL TRIAL

Document Date: September 14, 2017

Statistical Analysis Plan (SAP)

Intention-to-treat analysis. No intermediate analysis is planned. A bilateral significance level of 5%, 95% CI and 80% power will be used. The SPSS V21 program will be used. Analysis of efficacy of unadjusted parallel clinical trials. Data will be analyzed according to the CONSORT guidance and comparisons between groups will be based on the intention-to-treat principle. First: analysis of the baseline comparability of the study groups in relation to the variables studied. Descriptive statistics of all variables collected. The Student's t test or the Mann-Whitney U test (according to the frequency distribution of the variables studied) will be used to compare continuous variables, and Chi-square or Fisher's exact test for comparison of categorical variables.

In the case of finding a very different distribution of the independent baseline variables (1st visit) between the two groups, which would indicate an obvious selection bias despite randomization, the possibility of analyzing as a cohort study by means of propensity score techniques .

- Main objective "To assess the effect of brief oral and written information on the Advance Directives (ADs) given by primary care physicians, compared to usual clinical practice, on the proportion of persons interested in or performing VAD in 3 months in a heterogeneous group of patients (different ages and ethnicities) who go to a previous appointment ": inferential analysis of effectiveness, analysis of proportions of two samples. A multivariate logistic regression analysis with the variables of interest or realization of the yes / no VAS as the dependent variable will be performed and the group assigned as an independent variable, adjusting for the potential confounding factors.
- Secondary objectives: demographic and clinical characteristics that are considered likely to be associated with the completion of a priori VAD or that differ between study groups will be included in the logistic regression model for the dichotomous dependent variable.

1 · "Evaluate the baseline characteristics of those who perform or are interested in the VAD of both the control group and the intervention group": descriptive analysis for independent quantitative variables (age, number of children) and for qualitative variables , studies, comorbidity, religion, testament, marital status), frequency tables. Bivariate analysis using as a dependent variable the answer yes or no to the realization of the DVA or interest by DVA and as independent variables the basal characteristics. The Student's t test or the Mann-Whitney U test (according to the frequency distribution of the variables studied) will be used to compare continuous variables, and Chi-square or Fisher's exact test for comparison of categorical variables.

2 · "Evaluate the baseline characteristics of those who perform the VAD and those who are not in the intervention group": descriptive analysis for independent quantitative variables (age, number of children) and for qualitative variables

(gender, race, comorbidity, religion, testament, marital status), frequency tables. Bivariate analysis using as a dependent variable the answer yes or no to the realization of the VAD within the intervention group and as independent variables the basal characteristics. The Student's t test or the Mann-Whitney U test (according to the frequency distribution of the variables studied) will be used to compare continuous variables, and Chi-square or Fisher's exact test for comparison of categorical variables.

3 · "Evaluate the reasons why the document is formalized by open question": it will be categorized if there is a limited number of categories of responses and a descriptive univariate analysis will be done (frequency tables). In case of multiple answers the reasons will be described qualitatively.

4 · "Evaluate the average time to perform the DVA from the day of recruitment of the patient.": Univariate descriptive analysis.

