Patients will be randomized according to the list of random numbers guarded by a professional (or several) other than the study that will be located in the adjacent consultation. In case there is no professional close, the list will be delivered with a

closed envelope to another professional and will be contacted by telephone. Patients will be treated with the intervention when the number is 1 and control if it is 0. This number will be asked prior to the patient's entry into the consultation.

Predictive or independent variables to be obtained at the time of the first visit

For stratified analysis.

- Sex: Male, Female
- Race: Caucasian vs non-Caucasian
- Age in years
- Level studies: Primary, secondary, university, without studies.
- Comorbidity: measured by the Charlson index. Score: a) 0-1: no comorbidity; b) 2: low comorbidity; c) ≥ 3 : high comorbidity.
(Charlson.webloc calculator).
- Testament on material goods: Yes, no.
- Religious Confession: yes, no. Is considered a practitioner: yes, no
- Marital status: single, married, widowed, separated / divorced
- Number of children

To obtain this information will be extracted from the computerized medical history or the patient will be asked.

Intervention

Patients who are included in the intervention group, if they meet the inclusion criteria and do not present any exclusion criteria, will be given brief information about the existence of the document of anticipated wills after resolving the reason for the visit for which they had come the patient. This information will not last more than 3 minutes and will not be repeated on successive visits within the recruitment period. Also, an informative triptych (see attachments) will be given to the patient so that he can read it at home. These leaflets have been made by the Department of Health of the Generalitat de Catalunya. They will be advised that we can extend the information if they are interested or help them to do the document in the near future if they want, we will inform you that we would wait for the answer before 3 months (24). In case of interest, you can leave your information in the User Service of the outpatient clinic by specifying name, telephone number and reference doctor or ask for an appointment again.

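### The adjusted logistic model lets chance baseline differences choose its covariates; if advance directive (AD) completion is modelled alone, about 13 to 14.5 ADs are expected and an empty control cell would leave no finite odds ratio

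*SAP*

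**What the plan says.** The SAP (and the identical section of the protocol) gives two analyses for the main objective. The first is "inferential analysis of effectiveness, analysis of proportions of two samples". The second is a logistic regression "with the variables of interest or realization of the yes / no VAS as the dependent variable", with "the group assigned as an independent variable, adjusting for the potential confounding factors". Earlier the SAP describes the efficacy analysis as "Analysis of efficacy of unadjusted parallel clinical trials" and names chi-square or Fisher's exact test for categorical comparisons. It does not say which of the two analyses is primary.

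The adjustment factors are not listed. The bullet headed secondary objectives says that characteristics thought likely to be associated with completion, "or that differ between study groups will be included in the logistic regression model". No limit on the number of covariates is given, and no sparse-data method is named for the model. On software: "The SPSS V21 program will be used".

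The protocol section on predictive or independent variables offers ten candidates, including "Level studies: Primary, secondary, university, without studies" and "Marital status: single, married, widowed, separated / divorced". The section on result or dependent variables lists interest and AD completion as separate yes/no outcomes. The sample size calculation uses completion alone.

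**The concern.** There are two distinct problems.

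- **Covariate rule.** In a randomised trial, baseline differences between arms arise by chance. A rule that adds a variable because it differs leaves the form of the adjusted analysis unknown until the data are seen. This holds for completion, interest or a composite.
- **Sparse outcome.** If completion is modelled alone, the plan's own rates imply very few ADs, nearly all in the intervention arm. With none in control, ordinary logistic regression has no finite group odds ratio and no upper confidence limit. A Wald p-value or interval taken from such a fit carries no information. A long covariate list on so few ADs also makes the likelihood-ratio test more liberal.

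At stake are the adjusted estimate and its 95% CI. Because neither analysis is named primary, there is also freedom to choose between an adjusted and an unadjusted result afterwards.

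**Working it through.** **Inputs (protocol, sample size calculation).** AD completion 7.8% versus 1%; two-sided alpha 0.05; power 80%; 10% loss; 165 per arm; Poisson approximation.

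**The plan's own figure.** n = (1.960 + 0.842)² × (p1 + p2)/(p1 − p2)² = 7.849 × 0.088/0.068² = 149.4 per arm; 149.4/0.9 = 166.0. The stated 165 is reproduced to within about one patient. After full 10% loss, 165 × 0.9 = 148.5; 148 is used below.

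**Expected ADs if completion is modelled alone.**
- 148 per arm: 148 × 0.088 = 13.0, of which 1.48 in control.
- 165 per arm: 165 × 0.088 = 14.5, of which 1.65 in control.

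**Ceiling on covariate parameters**, with the protocol's own categories: sex 1, race 1, age 1, studies 3, Charlson 2, testament 1, religious confession 1, practising 1, marital status 3, children 1. The sum is 15, before the group term. At that ceiling there are 13.0/15 = 0.87 to 14.5/15 = 0.97 ADs per covariate parameter.

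**Chance of no event in control**, (1 − p)^n. This does not depend on the covariates.

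| Control rate | n = 148 | n = 165 |
|---|---|---|
| 1% (plan) | 22.6% | 19.0% |
| 0.5% (assumed) | 47.6% | 43.7% |
| 2% (assumed) | 5.0% | 3.6% |
| 5% (assumed) | 0.05% | 0.02% |

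The protocol gives the control rate in its source study only as below 1%, hence the 0.5% row. The 2% and 5% rows also serve for a composite with interest, for which the documents give no rate.

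**What such a trial would look like.** Take 12/148 versus 0/148, with group alone in the model:
- likelihood-ratio chi-square 17.1, p = 0.00003; Fisher p = 0.0004;
- odds ratio infinite, profile-likelihood 95% lower limit 6.2, no upper limit;
- risk difference 12/148 = 8.1%, Newcombe 95% CI 3.9 to 13.6 points;
- Firth-penalised odds ratio 27, 95% CI 3.5 to about 3,500.

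**Type I error at a nominal 5%, both arms at 4.4%** (the mean of 7.8% and 1%; n = 148 / 165).

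| Test | Rejects |
|---|---|
| Likelihood ratio, group only (exact enumeration) | 6.1% / 5.9% |
| Likelihood ratio, 3 covariates (simulated) | 6.0% / 6.1% |
| Likelihood ratio, 15 parameters (simulated) | 7.3% / 7.5% |
| Firth, 15 parameters (simulated) | 4.3% / 4.7% |
| Fisher (simulated) | 2.3% / 2.5% |

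The simulations used 6,000 trials per sample size with assumed covariate distributions unrelated to the outcome; Monte Carlo standard error is about 0.2 to 0.3 points. A short list adds essentially nothing to the group-only rate. Only the rise to 7.3-7.5% reflects the long list.

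**Chance imbalance.** If "differ" meant p < 0.05 on ten independent variables (both assumptions), at least one would differ in 1 − 0.95^10 = 40% of trials.

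**The case against.** - **The outcome may be a composite.** The objective and the dependent variable both join interest and completion with *or*, and a composite is at least as natural a reading as two models. This stands. The 13 to 14.5 ADs and the 19-23% apply only if completion is modelled alone. That reading remains open because completion is a separate outcome and the sample size rests on it.
- **The test of effect is already protected.** The unadjusted comparison is listed first and Fisher's exact test is named. This also stands. A reader might infer that the trial could fail to show an effect in one case in five; the documents do not support that. In the example above, Fisher's test is decisive although the odds ratio is infinite.
- **The long covariate list does not cause the infinite odds ratio.** Correct. An empty control cell has the same consequence with no covariates, and shortening the list would not prevent it.
- **Fifteen parameters is a ceiling.** Nothing says every variable will enter, and the study hypothesis names only six factors. It would be wrong to read the plan as a 15-parameter model. Equally, nothing limits the list.
- **The imbalance rule sits under secondary objectives.** True, but it refers to *the* logistic regression model, and the only such model introduced before it is that of the main objective. Applying the rule there is a reasonable inference, not a certainty.

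**Conclusion.** The concern holds in limited form, as a cheap improvement.

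The rule admitting covariates because the groups differ is a fault on any reading of the outcome. The sparse-data problem is conditional. If completion is modelled alone and the control rate is 1%, there is a 19-23% chance that the adjusted odds ratio and its upper limit do not exist; the range is 44-48% at an assumed 0.5% and 4-5% at an assumed 2%. For a composite the risk is 4-5% at an assumed 2% control rate and under 0.1% at an assumed 5%.

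What is lost is the adjusted estimate and any Wald inference, not the planned unadjusted test. The effect of a long list on Type I error is modest (7.3-7.5% against about 6% with group alone) and rests on assumed covariate distributions.

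**What to change.** In the SAP:

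1. State whether interest and completion form one composite outcome or two outcomes.
2. For AD completion, name the already planned unadjusted comparison as primary: risk difference with a score-type 95% CI (such as Newcombe), plus Fisher's exact test.
3. Delete the rule that adds covariates because they differ between groups. Name a short list in advance, for example from the six factors in the study hypothesis (age, race, sex, children, will, comorbidity).
4. Keep the adjusted model as supportive, fitted by Firth-penalised logistic regression with profile-likelihood CIs.

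This is mostly wording. The costs are fewer adjustment covariates, possibly an add-on to SPSS for the penalised fit, and an odds ratio that stays very imprecise when no control AD occurs. That imprecision is why the risk difference should lead.

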EFFECTIVENESS OF A BRIEF INFORMATION ABOUT ADVANCE DIRECTIVES IN PRIMARY CARE: A RANDOMIZED CLINICAL TRIAL

Promoter of the study: Proposal of own initiative of the researcher [name] to present as thesis of the Master's Degree Design and Analysis of Clinical Investigations of the Official College of Physicians of Barcelona (COMB) of the thesis student [name].

Family Physicians' Team of the Basic Health Area Florida Nord de l'Hospitalet de Llobregat:

-	- [name]	- [name]
-	- [name]	- [name]
-	- [name]	- [name]
-	- [name]	

Study to be presented in the design phase to the Master of the COMB.

ABSTRACT

The knowledge and completion of advance directives (ADs) by the population is generally low. Primary care could develop a very important role to inform and assist in the preparation of this document because of its accessibility.

Objective: To evaluate the effectiveness of an oral brief information and a brochure administered in primary care to improve the proportion of ADs records.

Design: Randomized clinical trial.

Ambit: 7 offices from a urban health center in Hospitalet de Llobregat which serves about 25,000 users older than 18 years.

Material and methods

It will be administered randomly triptych and oral brief information about the existence of advance directives for people over 18 to attend the appointment of their family doctor for any reason (intervention group). It will be given the possibility of more extensive information if they wish and collaboration will be offered for the advance directive according to patient preferences. The control group will not receive any information. Follow-up: 3 months. Variables will be: number of people interested in ADs, number of ADs made and demographic data (gender, age, education level, race, comorbidities, religion, testament) in both groups. Statistical analysis: multiple linear regression, Poisson and Cox as response analyzed, with the intervention/control group as the main variable adjusting for potential confounders. Bivariate comparison using Student t test or Mann-Whitney test (continuous variables) and chi-square or Fisher's exact test (categorical variables). 165 subjects were required in the control group and 165 in the intervention group.

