- Possible contamination of the groups when living in the same neighborhood and the possibility of communication between the patients in the control group and the intervention group. To find out this, patients in the control group will be asked to become interested or to do DVA if they have been informed by other patients of the study through the questions: Do you know anyone else who participates in this study? Did you talk about the study with that person?

- Bias of hyper-attendees: they are more likely to be chosen for the study however this problem is within usual clinical practice. The information will not be repeated to the patient who has already been randomized.

The study has been submitted to the Ethical Committee for Clinical Research (CEIC) of the University Institute for Research in Primary Care (IDIAP) Jordi Gol, and is awaiting the results of its evaluation. When accessing the eCAP and / or performing a personal interview to complete information on the variables is required, the patient's signed informed consent will be requested through his physician. The confidentiality of the subjects included in the study will be

guaranteed according to the Organic Law on Protection of Personal Data (15/1999 of December 13, LOPD). Researchers are committed to maintaining the confidentiality of information, working with anonymous patient data, and respecting current ethical and research practice standards.

Statistical Analysis Plan (SAP)

Intention-to-treat analysis. No intermediate analysis is planned. A bilateral significance level of 5%, 95% CI and 80% power will be used. The SPSS V21 program will be used. Analysis of efficacy of unadjusted parallel clinical trials. Data will be analyzed according to the CONSORT guidance and comparisons between groups will be based on the intention-to-treat principle. First: analysis of the baseline comparability of the study groups in relation to the variables studied. Descriptive statistics of all variables collected. The Student's t test or the Mann-Whitney U test (according to the frequency distribution of the variables studied) will be used to compare continuous variables, and Chi-square or Fisher's exact test for comparison of categorical variables.

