In the case of finding a very different distribution of the independent baseline variables (1st visit) between the two groups, which would indicate an obvious selection bias despite randomization, the possibility of analyzing as a cohort study by means of propensity score techniques .

- Main objective "To assess the effect of brief oral and written information on the Advance Directives (ADs) given by primary care physicians, compared to usual clinical practice, on the proportion of persons interested in or performing VAD in 3 months in a heterogeneous group of patients (different ages and ethnicities) who go to a previous appointment ": inferential analysis of effectiveness, analysis of proportions of two samples. A multivariate logistic regression analysis with the variables of interest or realization of the yes / no VAS as the dependent variable will be performed and the group assigned as an independent variable, adjusting for the potential confounding factors.
- Secondary objectives: demographic and clinical characteristics that are considered likely to be associated with the completion of a priori VAD or that differ between study groups will be included in the logistic regression model for the dichotomous dependent variable.

1 · "Evaluate the baseline characteristics of those who perform or are interested in the VAD of both the control group and the intervention group": descriptive analysis for independent quantitative variables (age, number of children) and for qualitative variables , studies, comorbidity, religion, testament, marital status), frequency tables. Bivariate analysis using as a dependent variable the answer yes or no to the realization of the DVA or interest by DVA and as independent variables the basal characteristics. The Student's t test or the Mann-Whitney U test (according to the frequency distribution of the variables studied) will be used to compare continuous variables, and Chi-square or Fisher's exact test for comparison of categorical variables.

2 · "Evaluate the baseline characteristics of those who perform the VAD and those who are not in the intervention group": descriptive analysis for independent quantitative variables (age, number of children) and for qualitative variables (gender, race, comorbidity, religion, testament, marital status), frequency tables.

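### The main objective has three listed analyses and none that decides, and covariates may enter the model because the arms are seen to differ

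*SAP*

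**What the plan says.** The SAP and the protocol section headed Statistical Analysis Plan carry the same text.

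- **Unadjusted analysis.** Under the main objective: "inferential analysis of effectiveness, analysis of proportions of two samples". No test is named there. The only tests given for categorical data come earlier, in the general paragraph: "Chi-square or Fisher's exact test for comparison of categorical variables", with no rule for choosing between them.
- **Adjusted analysis.** The next sentence adds a multivariate logistic regression of interest or completion, "and the group assigned as an independent variable, adjusting for the potential confounding factors". No covariates are listed.
- **Conditional analysis.** "In the case of finding a very different distribution of the independent baseline variables (1st visit) between the two groups", the plan keeps open "the possibility of analyzing as a cohort study by means of propensity score techniques". No threshold is given for the switch, and nothing says whether it would replace or supplement the other two.
- **Covariate rule.** Under the secondary-objectives bullet, the model takes characteristics thought likely to be "associated with the completion of a priori VAD or that differ between study groups will be included in the logistic regression model".
- **Hint of a hierarchy.** The opening paragraph contains the fragment "Analysis of efficacy of unadjusted parallel clinical trials". It leans towards an unadjusted analysis but does not say that this analysis decides.
- **Abstract.** The protocol abstract announces "multiple linear regression, Poisson and Cox as response analyzed, with the intervention/control group as the main variable adjusting for potential confounders". None of these three models appears in the SAP, and the SAP's logistic model does not appear in the abstract.

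**The concern.** Two choices are left until after the data are available.

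First, the unadjusted, adjusted and propensity-score results can differ, and the plan does not say which is the trial's result. Someone who has seen all three could settle it then, and the 5% level holds only for an analysis fixed in advance.

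Second, letting a variable into the model because the arms differ on it makes the adjusted result depend on the observed data. Under valid randomisation such differences are chance and carry no information on whether the variable predicts the outcome. They could also come from exclusions after allocation: the protocol's Intervention section removes control patients who ask for the information. In that case adjustment does not bring those patients back.

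**Working it through.** **1. The plan's own sample size.** Inputs from the protocol's sample-size paragraph: 7.8% against 1%, two-sided 0.05, power 80%, 10% loss, Poisson approximation.

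n = (z₀.₉₇₅ + z₀.₈₀)² (p₁ + p₂) / (p₁ − p₂)² = 2.8016² × 0.088 / 0.068² = 149.4 per arm; 149.4 / 0.90 = 166.0.

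The stated 165 is reproduced to within rounding. The formula is for an unadjusted two-group comparison, so naming that comparison as deciding leaves N unchanged.

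**2. Which model the covariate rule governs.** Secondary objectives 1 to 4 use only descriptive or bivariate methods. The only logistic model the SAP describes is the one for the main objective. The rule therefore most naturally governs that model, although it stands under the secondary-objectives bullet. This is an inference, but a strong one.

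**3. How often chance imbalance triggers the rule.** The protocol's list of independent variables has 9 bullets, or 10 variables if practising religion is counted separately. The plan does not define what counts as differing; p<0.05 and independent variables are assumed here.

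1 − 0.95⁹ = 0.370; 1 − 0.95¹⁰ = 0.401.

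**4. Cost of an open choice.** Null simulation with 165 per arm and 2,500 to 3,000 replicates per scenario (Monte Carlo standard error about 0.5 point). Assumptions: nine independent normal covariates, four of them prognostic, and an adjusted model using those four. The documents give no rate for the composite, so the event probability is varied.

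| Event probability at mean covariates | Log odds ratio per SD | Unadjusted alone | Adjusted alone | Better of the two | Also propensity weighting |
|---|---|---|---|---|---|
| 4.4% | 0.4 | 4.7% | 4.0% | 5.6% | 6.1% |
| 4.4% | 0.8 | 4.9% | 4.6% | 6.8% | 7.1% |
| 10% | 0.4 | 4.8% | 4.6% | 5.9% | 6.3% |
| 10% | 0.8 | 5.1% | 4.9% | 7.5% | 7.6% |
| 30% | 0.4 | 5.2% | 4.9% | 6.9% | 7.0% |
| 30% | 0.8 | 5.4% | 5.4% | 8.0% | 8.0% |

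The model with imbalance-selected covariates, taken alone, rejected 3.6% to 4.9% of the time. The inflation comes from the free choice among analyses, not from any one of them.

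**5. Secondary check: AD completion alone, at 7.8% against 1%.** Exact enumeration of all 2×2 tables, with 149 (165 less 10%) or 165 per arm:

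- No completion in the control arm: 0.99¹⁴⁹ = 22.4%; 0.99¹⁶⁵ = 19.0%. The maximum-likelihood odds ratio is then infinite, while the risk difference keeps an interval. For example, 12/149 against 0/149 gives 8.1 points, Newcombe 95% CI 3.8 to 13.5.
- Power of Pearson chi-square without continuity correction: 87.0% / 90.6%. Power of Fisher: 78.9% / 84.1%. The two verdicts differ in 8.1% / 6.5% of trials.
- Expected events at 165 per arm: 165 × (0.078 + 0.01) = 14.5. All listed baseline variables, as categorised, use about 15 parameters plus group, so 14.5 / 16 ≈ 0.9 events per parameter. The covariate list has to be short.

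**The case against.** The best defence is that the plan leans towards the unadjusted test, through both the fragment on unadjusted efficacy analysis and the sample-size method. It also names candidate covariates in advance: the protocol lists the baseline variables, and its hypotheses say which are expected to predict completion. The propensity-score analysis is only a possibility. All of this is true. But a leaning is not a hierarchy, nothing links the candidate list to the model, and an option without a trigger is itself part of the open choice.

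Four stronger readings are tempting and are not supported.

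- A reader might infer that the logistic model and an exact test would reach different verdicts in about a quarter of trials (26.0% / 22.4% for AD completion). That needs a Wald test, which neither document names, and infinite fits counted as non-significant. By the likelihood-ratio test, a group-only logistic model differs from chi-square in only 3.0% / 1.9% of trials. The figure also says nothing about covariates or propensity scores.
- A reader might carry the AD-completion figures over to the main outcome. That outcome also counts interest, and no rate is stated for it. Under assumed rates of 20% and 3%, even the Fisher-against-Wald disagreement is about 1%.
- A reader might bracket the control rate with the survey figures of 0.5% and 1.9%. Those are the share of respondents who already had an AD, not new completions in 3 months, and patients who have one are excluded.
- A reader might take the abstract's linear, Poisson and Cox models as three more rivals for the main comparison. They may simply be meant for different response types. What stands is that the abstract and the SAP do not match.

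**Conclusion.** The point holds as a fault in pre-specification. For the main objective three analyses are listed and none decides, and the only covariate rule is partly data-driven. The size is modest: type I error of about 6% to 8% instead of 5% if the better of the unadjusted and adjusted results may count, under the assumed covariate effects and event rates. The 37% to 40% chance of at least one imbalance assumes independent variables and a p<0.05 criterion.

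For AD completion alone at the planning rates, the unmade choice between the two listed tests also matters for the stated 80% power: at 149 per arm, Fisher falls just below it and Pearson chi-square is above it. This does not show that the main composite is underpowered. The missing hierarchy and the covariate clause apply whatever the event rate. The change should be made, and confidence in the point is high.

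**What to change.** Keep the main outcome as stated, and change the following in the SAP and in the matching protocol text.

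- **Deciding analysis.** Name the already listed unadjusted two-sample comparison, by allocated arm, as the single deciding analysis. Name one test, for example Pearson chi-square without continuity correction. (The corrected version has Fisher's power, 78.9%, at 149 per arm for AD completion.) Report the risk difference with a Newcombe or score 95% CI as the estimate, not as a second decision rule.
- **Sensitivity analysis.** Give the logistic model this role, with a short covariate list fixed in advance on prognostic grounds from the protocol's baseline variables. Use penalised (Firth) or profile-likelihood inference if an arm has few or no events.
- **Deletions.** Remove the clause that admits variables on which the arms are found to differ, and the propensity-score switch. Keep the baseline table descriptive.
- **Abstract.** Align its analysis sentence with the SAP.

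A logistic model with covariates fixed in advance could also serve as the deciding analysis. The unadjusted comparison is preferred because it matches the sample-size method and gives an estimate even with no control events.

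The cost is wording only: no new patients, data or outcomes. There are three limits. Penalised regression may need software beyond SPSS V21. The change does not recover patients excluded after allocation. And the SAP is dated September 2017, while the protocol's schedule puts the results report in January-February 2017 but the last follow-up in December 2017. If outcome data had already been seen, the change cannot restore pre-specification and should be reported as made afterwards.
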